## **Study Protocol**

This is a double-blind randomized parallel assignment phase 3 interventional study. Patients with persistent AF with a duration of  $\geq 48$  hours undergoing elective electrical cardioversion (CV) will be randomized to TEE-guided versus anticoagulation-guided groups.

In the anticoagulation group, the patients are planned to receive warfarin for at least 3 weeks with an INR value between 2.0-3.0. Those who were unable to use or have contraindications to warfarin will receive novel oral anticoagulants (NOACs) at the recommended dose instead of warfarin for at least 3 weeks. If left atrial thrombus is detected by TEE, no CV will be performed. Other patients in the both groups will undergo electrical CV. After the CV, all the patients will be given warfarin or NOACs for at least 4 weeks and the decision to continue anticoagulant after this period was made based on patients' CHA2DS2-Vasc-score. Patients with a score of  $\geq 1$  in men and  $\geq 2$  in women will take anticoagulation. All the patients will undergo cranial MRI before and 1 week after CV.

Inclusion criteria includes patients with the age of more than 18 years who are planned to undergo electrical CV without anticoagulation use within 48 hours of randomization.

Exclusion Criteria includes urgent CV, patients who have non-MRI compatible implanted pace-makers or other metal devices, claustrophobia, haematological disorders disabling patients to receive anticoagulant agents, AF secondary to temporary causes, serious rheumatic heart valve disease, hyperthyroidism, history of malignancy, left atrium diameter  $> 55$  mm and ejection fraction  $< 0.25$ .

## **Cardioversion**

CV will be performed in the fasting state with sedation. R wave-synchronized biphasic direct-current shocks will be delivered in all the patients with the step-up protocol of 100, and 200 J with anterolateral approach. Successful cardioversion was defined as the presence of sinus rhythm lasting  $\geq 1$  minute after the shock.

## **MRI**

All the patients will undergo diffusion brain MRI before and 1 week after the CV to detect silent cerebral thromboembolic events.

## **Follow-up**

All the patients will be seen at the first week, first month and then every 3-month thereafter, and at any time the patient experienced any symptoms for 2 years. Complete physical exam including neurological exam will be performed in all the cases on the follow-up. Clinical thromboembolic events and bleeding events will be recorded.

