## **Outcome Measures**

Efficacy outcome measures: Clinical thromboembolic events including ischemic stroke/transient ischemic attack (TIA), other thromboembolic events or death during 2 years follow-up or acute silent cerebral thromboemboli detected by diffusion MRI at 1 week post-CV.

Safety outcome measures All the bleeding events will be recorded.

Combined outcome measures: Clinical efficacy events or major bleeding during 2 years' follow-up or silent cerebral thromboembolism detected by MRI.

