### **Statistical analysis plan**

The significance levels of the tests will be accepted as the P-value of  $<0.05$ . Categorical variables will be presented as percentages and will be compared with Chi-square test. Continuous variables will be expressed as mean  $\pm$  SD. Normality test will be used to test the distribution of continuous variables and variables with normal distribution will be compared with Student t-test and those without normal distribution will be compared with Mann-Whitney U test.

Risk factors for safety and efficacy end-points will be identified using logistic regression analysis. Variables with a p value  $<0.10$  in univariate analysis will be entered into multivariate analysis with stepwise backward elimination method.

The Kaplan-Meier method will be used to compare the probability of freedom from clinical combined end points during long-term follow-up. Intention-to-treat analysis will be performed for follow-up findings.

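### Does the unstated starting point for the 2-year follow-up and the Kaplan-Meier curves undermine the comparison of the two strategies?

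*Combined protocol and SAP*

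**What the plan says.** The schedule in the Follow-up section reads "All the patients will be seen at the first week, first month and then every 3-month thereafter". It covers 2 years and adds a visit whenever symptoms occur. It names no anchor. In Outcome Measures the clinical efficacy outcome runs to thromboembolic events "or death during 2 years follow-up", again with no start. The Statistical analysis plan uses Kaplan-Meier to "compare the probability of freedom from clinical combined end points during long-term follow-up" and closes by committing follow-up findings to intention-to-treat.

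Two items are tied to CV in so many words. One is the MRI component, "acute silent cerebral thromboemboli detected by diffusion MRI at 1 week post-CV". The other is treatment afterwards: "After the CV, all the patients will be given warfarin or NOACs for at least 4 weeks".

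The Study Protocol section shows why the two possible clocks differ. Patients enter "without anticoagulation use within 48 hours of randomization". In the anticoagulation group "the patients are planned to receive warfarin for at least 3 weeks with an INR value between 2.0-3.0", with a NOAC for the same minimum time where warfarin cannot be used. For the other strategy, "If left atrial thrombus is detected by TEE, no CV will be performed".

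**The concern.** Randomisation and CV are separate events here, and the gap between them differs by arm. The anticoagulation group apparently waits at least 3 weeks, while no minimum wait is given for the TEE group. Some TEE patients are never cardioverted. The wait belongs to one strategy and the refusal of CV to the other, so a fair comparison should count what happens in both.

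The visit pattern can be read as starting at CV: the first-week visit falls when the post-CV MRI is due, and the first-month visit roughly when the minimum post-CV anticoagulation ends. On that reading, strokes, deaths and bleeds before CV would go uncounted, mainly in the anticoagulation arm, and patients refused CV would drop off the curve. The analysis would then compare patients from CV onward, not the groups as randomised. Two analysts using the same text could count different events.

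**Working it through.** The plan gives no event rate, sample size or effect size, so it has no figure of its own to reproduce. The check has two parts: what the text supports, and how much the choice of clock could matter.

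**1. What the text supports**

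| Feature of the plan | Points to CV | Points to randomisation |
|---|---|---|
| First-week visit coincides with the 1-week post-CV MRI | yes | |
| First-month visit near the end of 4 weeks' post-CV treatment | weakly (4 weeks is a minimum, and a first-month visit is common in any schedule) | |
| Every patient is to be followed, including those refused CV | | yes (they have no CV date) |
| Intention-to-treat for follow-up findings | | yes |
| MRI and post-CV treatment are expressly dated from CV; the 2-year window is not | | yes (CV is named where it is meant) |

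The CV clock is an inference from matching visit times. Dropping patients refused CV would conflict with the intention-to-treat sentence. Leaving out pre-CV events is a softer conflict, because that sentence does not say when follow-up begins.

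**2. Scale**

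From the documents: the minimum lead-in is 21 days and the window 2 years, so 21 / 730.5 = 2.9%. That the lead-in follows randomisation is inferred from the entry criterion and the 3-week minimum. All other inputs below are assumptions.

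*Anticoagulation arm.* Assume a 10% 2-year risk, so weekly hazard h = -ln(0.90)/104, and lead-in hazard k times the later hazard. A CV clock drops 3 weeks at the start and adds 3 at the end.

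- CV clock: 1 - exp(-104h) = 10.00%
- Randomisation clock: 1 - exp(-(3k + 101)h)

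| k | Randomisation clock | CV minus randomisation |
|---|---|---|
| 0.5 | 9.86% | +0.14 points |
| 1 | 10.00% | 0 |
| 2 | 10.27% | -0.27 points |
| 5 | 11.09% | -1.09 points |

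*TEE arm.* Assume a share q = 5% is refused CV and dropped, with r times the 10% risk of the others. Change in arm risk = -q(r - 1) × 10%.

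| r | Change |
|---|---|
| 0.5 | +0.25 points |
| 1 | 0 |
| 2 | -0.50 points |
| 3 | -1.00 points |

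*Between arms (anticoagulation minus TEE).* The shifts fall on different arms and can offset each other:

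- k = 2, r = 2: -0.27 - (-0.50) = +0.23 points
- k = 5, r = 0.5: -1.09 - 0.25 = -1.34 points
- k = 0.5, r = 3: 0.14 - (-1.00) = +1.14 points

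The sign depends wholly on the assumed values.

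*Risk falling inside the lead-in.* With 2-year risk R between 4% and 12% and hazard per year -ln(1 - R)/2, the risk in 21 days is 0.12 to 0.37 points at constant hazard, and 0.6 to 1.8 points if early hazard is five times as high. These are events a CV clock would omit before the extra 3 weeks at the end are credited.

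*Wider TEE-arm inputs.* If 5% to 15% have thrombus, with 10% to 20% risk against 8% in the others, dropping them lowers the arm's risk by 0.05 × 2 = 0.1 to 0.15 × 12 = 1.8 points. This requires an exclusion that the intention-to-treat sentence rules out.

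**The case for a change.** The best case for a change is that intention-to-treat settles who is analysed and in which group, not when time starts. The schedule also fits neither clock cleanly. From CV, no scheduled visit covers the lead-in, so events there might never be recorded and no later analysis could restore them. From randomisation, the anticoagulation arm's first-week visit falls at least 2 weeks before CV (3 weeks less 1) and cannot be the visit for the post-CV MRI. A sentence naming the time origin would cost almost nothing.

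Part of this stands. The origin is unstated, and a sentence naming it would be harmless. Poor capture of lead-in events is a weaker point. The Follow-up section provides for visits whenever symptoms occur. All patients have an MRI before CV, and those going on to CV must attend for it, so a stroke, major bleed or death during the wait should come to light. That is a reasonable inference, not something the plan states.

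Reworking the schedule would do harm of its own. Telephone checks during the wait would fall mainly on the anticoagulation arm and make event detection unequal. Keeping the early visits on CV while running the 3-monthly visits from randomisation would put that arm's first-month visit at about week 7 (3 + 4) or later, not far from a 3-month visit at week 13, so spacing would differ by arm. Counting events from randomisation needs none of this.

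**Conclusion.** No change follows. The plan leaves a clock unstated; it does not choose a wrong one. Follow-up of every patient, together with intention-to-treat, leads a careful analyst to count clinical, bleeding and combined outcomes from randomisation and to keep the MRI timed from CV, which gives a sound comparison with the plan as written.

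The harm needs two further conditions: that someone adopts a CV clock the text does not state, and that risk differs between the lead-in and later, or between patients who are and are not cardioverted. If neither difference exists, the expected bias is zero. If one does, the shifts calculated on a 10% 2-year risk reach about 1 percentage point in an arm only at the extreme inputs (k = 5 or r = 3). The wider thrombus inputs reach 1.8 points, but only by excluding patients whom intention-to-treat keeps. The 21 days and the 2 years come from the documents; every risk and ratio is assumed, and neither size nor direction can be derived from the plan.

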## **Outcome Measures**

Efficacy outcome measures: Clinical thromboembolic events including ischemic stroke/transient ischemic attack (TIA), other thromboembolic events or death during 2 years follow-up or acute silent cerebral thromboemboli detected by diffusion MRI at 1 week post-CV.

Safety outcome measures All the bleeding events will be recorded.

Combined outcome measures: Clinical efficacy events or major bleeding during 2 years' follow-up or silent cerebral thromboembolism detected by MRI.

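### Non-bleeding complications of TEE, a procedure specific to one randomised strategy, are not named for collection, so the plan cannot support a full safety comparison

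*Combined protocol and SAP*

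**What the plan says.** Under Study Protocol, patients "will be randomized to TEE-guided versus anticoagulation-guided groups". In the anticoagulation arm "the patients are planned to receive warfarin for at least 3 weeks with an INR value between 2.0-3.0", with a NOAC where warfarin is unsuitable. CV is planned in both arms unless TEE shows a left atrial thrombus. The same section then puts both arms on anticoagulation: "After the CV, all the patients will be given warfarin or NOACs for at least 4 weeks", with continuation decided by the CHA2DS2-VASc score.

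On what is measured:

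- Outcome Measures, safety: "Safety outcome measures All the bleeding events will be recorded".
- Follow-up: "Clinical thromboembolic events and bleeding events will be recorded".
- Outcome Measures, efficacy: stroke or TIA, "other thromboembolic events or death during 2 years follow-up", or silent emboli on the 1-week MRI.
- Outcome Measures, combined: "Clinical efficacy events or major bleeding during 2 years' follow-up or silent cerebral thromboembolism detected by MRI".

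Under Cardioversion: "CV will be performed in the fasting state with sedation". Sedation for TEE is not mentioned. No section describes collection of adverse events, serious adverse events or procedural complications.

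**The concern.** Each strategy has a harm of its own. One arm has at least 3 more weeks of anticoagulation before CV, and its typical harm, bleeding, is the safety outcome. The other arm has an added invasive procedure. Some of that procedure's harm is captured, because TEE bleeding falls under all bleeding and a fatal complication falls under death. The rest, such as oesophageal or airway injury, aspiration or an unplanned admission, has no definition, no place in data collection and no analysis.

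At stake is what the trial may conclude about safety. A comparison that omits part of one strategy's specific harm may make that strategy look better than it is. The combined outcome has the same gap, since it adds only major bleeding to the efficacy events. Events that are not collected prospectively in both arms cannot be rebuilt reliably at analysis.

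**Working it through.** The plan states no sample size, event rate or margin, so there is no figure to reproduce. The check has three parts.

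**1. Which harms can be counted?** Setting Follow-up and Outcome Measures side by side:

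| Harm | Counted? | Where |
|---|---|---|
| Bleeding, including from TEE | Yes | Safety; major bleeding also in combined |
| Clinical thromboembolism | Yes | Efficacy, combined |
| Death from any cause, including a procedure | Yes | Efficacy, combined |
| Non-bleeding, non-embolic, non-fatal TEE complication | Not named | – |
| The same kind of complication of sedation or shock at CV | Not named | – |

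The last row applies to both arms, because CV is planned in both. The row above it applies to the TEE arm, assuming that TEE is routine only there, as the group names imply.

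**2. How far do the arms differ in anticoagulant exposure?** Inputs from Study Protocol: at least 3 weeks before CV in one arm and at least 4 weeks after CV in both. I assume no anticoagulation before CV in the TEE arm, which the documents do not state.

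- Minimum course: 3 + 4 = 7 weeks v 4 weeks, ratio 7/4 = 1.75.
- Treatment through 2 years after CV: 3 + 104 = 107 v 104 weeks, ratio 107/104 = 1.03.

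Bleeding is thus a harm of both arms. Only the lead-in differs by design.

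**3. How might the counted and omitted harms compare?** All rates here are assumptions.

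*Major bleeding* at 2% to 4% per year, extra risk = rate × 3/52:

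- 0.02 × 3/52 = 0.12 percentage points
- 0.04 × 3/52 = 0.23 percentage points

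*Any bleeding* at 5% to 20% per year on treatment, constant hazard, risk = 1 − exp(−h·t) with h = annual rate/52 and t in weeks:

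| Annual rate | 7 v 4 weeks | Difference | 107 v 104 weeks | Difference |
|---|---|---|---|---|
| 5% | 0.67% v 0.38% | 0.29 points | 9.78% v 9.52% | 0.26 points |
| 10% | 1.34% v 0.77% | 0.57 points | 18.60% v 18.13% | 0.47 points |
| 20% | 2.66% v 1.53% | 1.13 points | 33.74% v 32.97% | 0.77 points |

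*Uncounted TEE complications* at 0.1% to 1% of TEE-arm patients, as a ratio to the extra bleeding:

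- Against major bleeding: from 0.1/0.23 = 0.4 to 1/0.12, about 8.
- Against any bleeding, the safety outcome as defined: from 0.1/1.13 = 0.09 to 1/0.26 = 3.8.

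Both ranges span 1, so these assumptions do not settle which harm is larger.

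**Time zero.** Follow-up lasts 2 years, but the plan does not say whether it runs from randomisation or from CV. From randomisation, lead-in bleeding counts against the anticoagulation arm while a non-bleeding TEE injury does not count against the TEE arm. From CV, lead-in bleeding may also go uncounted, and the imbalance shrinks or disappears. In that case neither arm's specific harm is fully measured.

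**The case against.** A reader might infer that the safety comparison is tilted towards TEE by construction, that no harm of TEE is counted, or that the omitted harm would reverse the result. The documents do not support these readings, for four reasons.

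- TEE bleeding and death are counted, so the gap is only the non-bleeding, non-embolic, non-fatal remainder.
- Both arms are anticoagulated after CV, so bleeding does not belong to one arm alone. With treatment through 2 years, planned exposure differs by about 3%.
- Sedation is stated only for CV, which is planned in both arms. Its omission is a gap in completeness and is not shown to favour either arm.
- Time zero is unstated, and the MRI and early visits could suggest counting from CV. A change of sign needs particular combinations of assumed rates. At 0.1%, the omitted harm is below even the lower major-bleeding figure of 0.12 points.

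It can also be said that the follow-up wording does not say that only these events are recorded, and that visits include a complete physical examination and are allowed whenever symptoms occur. That is fair: an investigator might note a TEE injury. But without a definition or an instruction to record it in both arms, such notes would not give a comparable count.

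These objections narrow the point to its stated form. They do not remove it, because a complication type specific to one randomised strategy still has no planned collection.

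**Conclusion.** The point holds in limited form. The plan names bleeding and thromboembolism for recording and counts death under efficacy. It leaves out non-bleeding, non-embolic, non-fatal complications of TEE. This may favour the TEE strategy, and the plan as written cannot support a full safety comparison of the two strategies.

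The size and direction of any effect are unknown. The documents give no complication or bleeding rates and no time zero, and the illustrative ranges above are compatible with the omitted harm being either smaller or larger than the extra bleeding. The conclusion rests on TEE being routine only in the TEE-guided arm. It does not rest on any of the assumed rates.

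The efficacy comparison is not affected. This is an inexpensive improvement worth making, not a flaw that undermines the trial.

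**What to change.** In Follow-up and Outcome Measures:

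- Add a separate safety outcome of serious non-bleeding complications of TEE, sedation and cardioversion, defined as those resulting in admission, prolonged stay or intervention. Deaths are already counted and need not be repeated here.
- Record it in both arms from randomisation to 1 week after CV. Where no CV is done, for example because TEE shows a thrombus, record it to 1 week after TEE.
- State that bleeding is also counted from randomisation, so that the lead-in period is included.
- Report these complications by arm beside bleeding. Leave the combined outcome unchanged: adding them to it would be a debatable choice, and separate reporting is enough to meet the concern.

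The window from randomisation is longer in the anticoagulation arm because of the lead-in. That is part of the strategy being compared, and the report should say so.

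The cost is protocol wording and a few form fields at TEE, at CV and at the 1-week visit. Patients who have TEE but no CV need an equivalent 1-week contact if the existing visit does not cover them. The other downside is a TEE safety figure that may be less favourable than bleeding alone would show.

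### The protocol and SAP name no primary outcome and no testing order, so any of two or three overlapping composites could be claimed as the trial's result at P<0.05

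*Combined protocol and SAP*

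**What the plan says.** The Outcome Measures section of the combined protocol and SAP sets out three groups of outcomes.

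- Efficacy: "Efficacy outcome measures: Clinical thromboembolic events including ischemic stroke/transient ischemic attack (TIA), other thromboembolic events or death during 2 years follow-up", with an imaging component added: "or acute silent cerebral thromboemboli detected by diffusion MRI at 1 week post-CV".
- Safety: "Safety outcome measures All the bleeding events will be recorded".
- Combined: "Combined outcome measures: Clinical efficacy events or major bleeding during 2 years' follow-up or silent cerebral thromboembolism detected by MRI".

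None is called primary or secondary. The supplied text also contains no hypothesis and no sample-size calculation that would show indirectly which outcome is meant to decide the trial.

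The Statistical analysis plan sets a single threshold of 0.05 for tests in general ("The significance levels of the tests will be accepted as the P-value of" and so on). It gives no testing order, no division of the significance level and no adjustment. It names these analyses that could apply to the outcomes:

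- "Categorical variables will be presented as percentages and will be compared with Chi-square test"
- "Risk factors for safety and efficacy end-points will be identified using logistic regression analysis"
- "The Kaplan-Meier method will be used to compare the probability of freedom from clinical combined end points during long-term follow-up"

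The end point in the last of these carries a label that the Outcome Measures section does not use.

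**The concern.** The composites overlap but answer different questions. The efficacy outcome asks about thromboembolism and death, including silent lesions on MRI. The combined outcome asks about net benefit, because it also counts major bleeding. The Kaplan-Meier end point most likely asks about net clinical benefit without the imaging lesions. A strategy that reduces emboli but increases bleeding could succeed on one and fail on another, and the plan has no rule for which result then stands.

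There are two consequences. First, the reported conclusion can depend on a choice made after the results are known. Second, if any significant composite may be claimed, the chance of a false-positive trial exceeds the 5% that a single test carries.

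**Working it through.** **Inputs from the documents.** Each test is at 0.05. The efficacy composite (E) is clinical events or MRI lesions. The combined composite (C) is E or major bleeding. The Kaplan-Meier end point (K) is undefined and is read here as clinical efficacy events or major bleeding, without MRI lesions. The plan states no overall error rate, so there is no figure of its own to reproduce.

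**Inputs that are assumed**, because the documents give no rates or sample size: 75, 150 or 300 patients per arm; E at 10, 15 or 20%; major bleeding at 2 or 5%, independent of E; clinical events making up 25, 50 or 75% of E. This gives 3 × 3 × 2 × 3 = 54 settings.

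**Step 1: upper bounds if the tests were independent.**

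- Two tests: 1 − 0.95² = 0.0975.
- Three tests: 1 − 0.95³ = 0.1426.

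The composites share events, so the true figures are lower.

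**Step 2: how strongly E and C are correlated.** Because E is contained in C, the correlation is √[p_E(1 − p_C) / (p_C(1 − p_E))], with p_C = 1 − (1 − p_E)(1 − p_bleed).

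- E 10%, bleeding 5%: p_C = 1 − 0.90 × 0.95 = 0.145. Correlation = √[(0.10 × 0.855)/(0.145 × 0.90)] = 0.81.
- E 20%, bleeding 2%: p_C = 1 − 0.80 × 0.98 = 0.216. Correlation = √[(0.20 × 0.784)/(0.216 × 0.80)] = 0.95.

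**Step 3: chance of at least one p<0.05 with no true difference.** Each setting was simulated 100,000 times using Pearson chi-square tests. The Kaplan-Meier comparison was approximated by 2-year proportions.

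| Claim allowed on | Simulation | Multivariate normal check |
|---|---|---|
| One composite alone | 4.7–5.3% | 5% by construction |
| E or C | 6.3–8.0% | 6.4–7.8% |
| E, C or K | 8.6–11.7% | 8.6–11.1% |
| Fixed order E, then C, then K | 4.8–5.3% | 5% by construction |

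The two-outcome figure is lowest at 300 per arm with E 20% and bleeding 2%, and highest at 75 per arm with E 10% and bleeding 5%. By clinical share of E, the three-outcome figure is 10.2–11.7% at 25%, 9.6–10.9% at 50% and 8.6–9.8% at 75%.

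**Step 4: sensitivity to the assumed rates.** A separate simulation used 100 or 200 per arm, clinical events 5–8%, MRI lesions 3–10% and major bleeding 3–8%. It gave about 7–8.5% for two composites and about 10–11% for three. Outside the main grid, the normal approximation for two composites gives 8.4% at E 5% and bleeding 5%, and just under 6% at E 30% and bleeding 1%.

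**Step 5: why a fixed order controls the error.** With no true difference, any claim first requires E to reject. The chance of any false claim therefore equals the single-test rate for E, 4.8–5.3%.

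**The case against.** Efficacy is listed first, which might be taken to mean that it is primary. But list order is not a designation, and the only time-to-event comparison the SAP specifies is for a combined end point, so the text points two ways.

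A primary outcome may be named elsewhere. One part of the document was removed before review and no registry record was available, so this point applies to the supplied text only. Even if a primary is registered, the SAP should state it and the testing order.

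The inflation figures depend on assumed inputs. This is right: they are not bounds for this trial, and other plausible rates move the two-composite figure somewhat outside the main range, as step 4 shows. Every setting examined still exceeds 5%.

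The third composite rests on an interpretation. This also stands. If the Kaplan-Meier end point is simply the listed combined outcome, there is no third composite, only a second analysis of the same one. The two-composite figure does not depend on this reading or on the Kaplan-Meier approximation.

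The MRI component is worded differently in the two composites: the efficacy outcome specifies acute lesions at the 1-week scan, while the combined outcome does not. Treating them as the same is the natural reading, but it is an assumption.

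Finally, naming the efficacy composite as primary does not finish the work. It has no assigned test, and its imaging part is timed from cardioversion, which patients with left atrial thrombus do not receive under the Study Protocol section. That is a separate gap and does not weaken this point.

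**Conclusion.** The concern holds. The supplied protocol and SAP do not say which outcome decides the trial, and the 0.05 rule as written lets any of the overlapping composites be claimed. Under the assumed rates and sample sizes, the false-positive chance is about 6–8% for the efficacy and combined outcomes. It is about 9–12%, roughly double the nominal 5%, if the Kaplan-Meier end point is a third composite without MRI lesions. The exact size depends on inputs the documents do not give. The lack of a deciding outcome does not, and it is the more serious part. The change should be made; it is a matter of specification and needs no redesign.

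**What to change.** 1. Name one primary outcome and one test for it at 0.05. The efficacy composite as now defined is one option; the choice is the sponsor's.
2. Place the other composites after it in a fixed order, for example the combined outcome and then the clinical combined Kaplan-Meier outcome. Test each only if the one before is significant. Otherwise report it with a 95% confidence interval and make no claim.
3. Report bleeding as a safety outcome with 95% confidence intervals, outside the testing order.
4. State in one line what the Kaplan-Meier end point is. If it means the clinical part of the combined outcome, without MRI lesions, say so. Confirm also that the MRI component is the same in both listed composites.
5. If the efficacy composite is chosen, state how its imaging part is defined for patients who are not cardioverted.

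The cost is protocol and SAP wording only, with no added visits, scans or patients. It must be fixed before unblinding; the documents do not give the trial's status. The downside is that a significant secondary outcome alone could no longer be presented as a positive trial.
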